14.1.35 Incomplete dates for last known date patient alive or death

All dates must be completed with day, month and year. If the day is missing, the 15th of the month will be used for incomplete death dates or dates of last contact.

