10.6.1.3 Progression-free survival

Progression-free survival (PFS) is the time from date of start of treatment to the date of event defined as the first documented progression or death due to any cause. If a patient has not had an event, progression-free survival is censored at the date of last adequate tumor assessment.

Disease progression will be assessed using the local (treating center's radiologist's) investigator's tumor assessment. PFS will be summarized using the Kaplan-Meier method. Percentiles (25%, median, 75%) of the event time distribution will be presented along with their two-sided 95% confidence interval. The Kaplan-Meier curve will be displayed graphically.

[figure not shown]

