- Date of last contact is defined as the last date the patient was known to be alive. This corresponds to the latest date for either the visit date, lab sample date or tumor assessment date. If available, the last known date patient alive from the survival follow-up page is used. If no survival follow-up is available, the date of discontinuation is used as last contact date.
- Date of secondary anti-cancer therapy is defined as the start date of any additional (secondary) antineoplastic therapy or surgery.

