14.1.33 Calculation of 'time to event' variables

Time to event = end date - start date + 1 (in days)

When no post-baseline tumor assessments are available, the date of randomization/start of treatment will be used as end date (duration = 1 day) when time is to be censored at last tumor assessment, i.e. time to event variables can never be negative.

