Total number of censored, n (%)	xx (xx.x)		xx (xx.x)		xx (xx.x)	
Percentiles (95%CI) (weeks) ^b						
25 th percentile	xx.x (xx.x, xx.x)		xx.x (xx.x, xx.x)		xx.x (xx.x, xx.x)	
Median	xx.x (xx.x, xx.x)		xx.x (xx.x, xx.x)		xx.x (xx.x, xx.x)	
75 th percentile	xx.x (xx.x, xx.x)		xx.x (xx.x, xx.x)		xx.x (xx.x, xx.x)	

Asian: Indonesia, India, Vietnam, Turkey, South Korea, Thailand, Malaysia, Taiwan or Jordan.

Non-Asian: Australia, Morocco, South Africa or Tunisia.

^aTime to deterioration is the time from date of start of treatment to the date of the event defined as deterioration. Deterioration defined as an increase in performance status from 0 to 2 or greater, an increase in performance status from 1-2 to 3 or greater, or death due to any cause.

^bPercentiles with 95% CIs are calculated from PROC LIFETEST output using method of Brookmeyer and Crowley (1982).

^cEvent-free probability estimate is the estimated probability that a patient will remain event-free up to the specified time point. Event-free probability estimates are obtained from the Kaplan-Meier survival estimates.

Table 7.3.2 Time to Deterioration of ECOG Performance Status Overall and in Asian Subgroup - Per Protocol Set

This table will be created using the same layout as Table 7.3.1.

Table 7.3.3 Distribution of Time to Deterioration of ECOG Performance Status Overall and in Asian Subgroup by Analysis Set

Statistics	Asian (N=xx)		Non-Asian (N=xx)		Total (N=xxx)	
	Full analysis set Time in weeks (95% CI)	Per protocol set Time in weeks (95% CI)	Full analysis set Time in weeks (95% CI)	Per protocol set Time in weeks (95% CI)	Full analysis set Time in weeks (95% CI)	Per protocol set Time in weeks (95% CI)
25% Deterioration	xx (xx.x, xx.x)	xx (xx.x, xx.x)	xx (xx.x, xx.x)	xx (xx.x, xx.x)	xx (xx.x, xx.x)	xx (xx.x, xx.x)
50% Deterioration	xx (xx.x, xx.x)	xx (xx.x, xx.x)	xx (xx.x, xx.x)	xx (xx.x, xx.x)	xx (xx.x, xx.x)	xx (xx.x, xx.x)
75% Deterioration	xx (xx.x, xx.x)	xx (xx.x, xx.x)	xx (xx.x, xx.x)	xx (xx.x, xx.x)	xx (xx.x, xx.x)	xx (xx.x, xx.x)

Asian: Indonesia, India, Vietnam, Turkey, South Korea, Thailand, Malaysia, Taiwan or Jordan.

Non-Asian: Australia, Morocco, South Africa or Tunisia.

CI: Confidence Interval

Table 8.1.1 Best Overall Response Rate *Overall and in Asian Subgroup* - Full Analysis Set

Everolimus + Exemestane (N=xxx)	Asian (N=xx)		Non-Asian (N=xx)		Total (N=xxx)	
	n(%)	(95% CI)	n(%)	(95% CI)	n(%)	(95% CI)

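### A death date with a missing day is set to the 15th with no lower bound, so death can be placed before a date on which the patient is documented alive

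*Protocol*

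**What the plan says.** Protocol Appendix 1, Section 14.1.35, opens with a completeness requirement, "All dates must be completed with day, month and year", and then gives the fallback: "If the day is missing, the 15th of the month will be used for incomplete death dates or dates of last contact". It attaches no condition relating to first dose, last visit, last laboratory sample or last scan.

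Section 14.1.33 computes every time-to-event variable as end date minus start date plus one day.

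Death enters two planned time-to-event outputs. PFS (Protocol Section 10.6.1.3) runs from treatment start to "the date of event defined as the first documented progression or death due to any cause". In the SAP, the footnote to Table 7.3.1 counts as ECOG deterioration, besides a rise from 0 to 2 or more, "an increase in performance status from 1-2 to 3 or greater, or death due to any cause". SAP Table 8.3.1 reports PFS events separately as progressions and deaths, and Table 6.10 lists the day of death relative to the start of study drug.

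The SAP text available here consists of reporting conventions and shells for tables, figures and listings. It contains no date-imputation rule.

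**The concern.** A mid-month default is a reasonable guess when nothing else is known about the month. It is not reasonable when the database already holds a later date in that month on which the patient was alive. Applied literally, the rule then contradicts recorded data in one of three ways:

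- death falls before a scan, visit, sample or dose in the same month, so the event time is too short;
- death falls before a documented progression, so both the time and the type of the PFS event change;
- death falls before the first dose, so the time is zero or negative.

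At stake are a few event times in PFS and time to ECOG deterioration, the split between progressions and deaths in Table 8.3.1, and the relative day of death in Table 6.10.

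**Working it through.** The plan states no figure on this point, so there is nothing to reproduce beyond the formula. As a check on it, Section 14.1.33 gives a duration of 1 day when the end date equals the start date, and end minus start plus one does give 1.

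**Illustrative cases.** The dates are assumptions. In each case the day of death is missing and is imputed as 15 March.

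| Case | Start | Known date | True death | Time as imputed | Correct time |
|---|---|---|---|---|---|
| A | 20 March | first dose, 20 March | 28 March | 15 − 20 + 1 = −4 days | 28 − 20 + 1 = 9 days |
| B | 6 January | scan with stable disease, 24 March | 30 March | 69 days | 84 days |
| C | 6 January | scan with progression, 18 March | 30 March | death at 69 days | progression at 72 days |

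In case B the imputed death is 24 − 15 = 9 days before a scan at which the patient was alive and progression-free, and PFS is 84 − 69 = 15 days too short. In case C the change in time is only 72 − 69 = 3 days, but a documented progression becomes a death in Table 8.3.1.

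**Bounds on the error.** A true death on the 31st is imputed 31 − 15 = 16 days early, and one on the 1st is imputed 15 − 1 = 14 days late. If the first dose was on the 16th the time is 15 − 16 + 1 = 0, and if it was on the 31st it is 15 − 31 + 1 = −15 days.

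**How often the ordering fails, given a missing day.**

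- Take last contact day L and death day D in the same 30-day month, with L no later than D and all ordered pairs equally likely. There are 30 × 31 / 2 = 465 pairs. Those with L after the 15th number 15 + 14 + … + 1 = 120, and 120 / 465 = 26%. The same count applies if L is the day of first dose.
- Alternatively, take the death day as uniform over a 30-day month and last contact k days earlier. The share is (15 − k) / 30: 47% for k = 1, 33% for k = 5, 27% for k = 7, 17% for k = 10 and 3% for k = 14.
- If instead last contact is uniform over the 10-week visit interval, the share is 120 / (30 × 70) = 5.7% of missing-day deaths.

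**As a share of all deaths.** The documents do not say how many deaths lack a day. Assuming 2% to 10%, the 5.7% figure gives about 0.1% to 0.6% of deaths. The 26% figure gives about 0.5% to 2.6%, and that is only if every such death has a last contact in the same month.

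**The case against.** The strongest reply is that this will hardly ever matter. Full dates are required, so imputation is a fallback. Protocol Sections 9.3 and 9.4 provide automatic discrepancy checks and site queries before lock, and a death dated before a visit is an obvious query. Section 14.1.27 calls these programming rules guidance, Section 14.1.28 leaves study-specific decisions to the protocol or the reporting and analysis plan, and Section 14.1.37 expects programs to be adapted. Fatal events up to 30 days after treatment are mostly reportable within 24 hours, so their dates should usually be known. All of this stands, and it is why the point is minor. It does not remove the gap: when a site cannot supply the day, the stated rule decides. Deaths from progression documented by RECIST are exempt from SAE reporting (Section 8.1.1). Such patients normally have a PFS event already, but case C shows that an imputed death can still displace it.

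Three stronger readings are tempting, and the documents do not support them.

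- A reader might infer that the rule contradicts Section 14.1.33, which says "time to event variables can never be negative". That clause closes a sentence about patients with no post-baseline tumour assessment who are censored at treatment start. It neither limits imputed death dates nor is breached by them.
- A reader might infer that the rule bypasses data cleaning. The completeness requirement, the query process and the guidance status of the section say otherwise.
- A reader might infer that imputing last contact as the 15th does the same harm. Section 14.1.24 already builds last contact from recorded dates: "This corresponds to the latest date for either the visit date, lab sample date or tumor assessment date". It also says "If available, the last known date patient alive from the survival follow-up page is used", which could let an imputed 15th override a later visit, but Table 7-1 schedules no survival follow-up. PFS is censored at the last adequate tumour assessment, and no listed endpoint is stated to use last contact.

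**Conclusion.** The gap is real as written. For a death with a missing day, Section 14.1.35 can yield a date that the trial's own records rule out, and no floor appears in the text available. Because the SAP is available only in part, a floor could exist in material not seen, so the claim goes no further than that.

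The consequence is small. Any one event time is at most 16 days too early, and the error arises only when the day is missing and the patient has a documented date after the 15th of the same month. The non-positive time further requires death in the same month as a first dose after the 15th. The 26% is not a share of all deaths: it is conditional on a missing day and a same-month last contact, under equally likely day pairs. The 2% to 10% range for missing days is an assumption. The study tests no hypothesis (Protocol Section 10.7), its primary objective is safety, and overall survival is not a listed endpoint. This is a correction worth making because it is nearly free; it does not threaten the conclusions.

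**What to change.** Add one sentence to Section 14.1.35 or to the SAP: a missing day of death is imputed as the later of the 15th and the last date in that month on which the patient is documented alive (dose, visit, laboratory sample or tumour assessment), never before treatment start and never beyond the end of the recorded month. If the result coincides with a documented progression, count the event as progression.

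Under this rule, case A becomes 1 day instead of −4. Case B becomes 78 days instead of 69, leaving an error of 84 − 78 = 6 days rather than 15. Case C stays a progression at 72 days.

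Using the day after the last documented date would be a poorer choice. It forbids death on the day of last contact, and for a contact on the last day of the month it moves the death into the next month, against the recorded month. The last-contact rule needs no change for the listed endpoints.

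The cost is one sentence and one line of code, with no new data collection.

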14.1.36 Non-target lesion response

If no non-target lesions are identified at baseline (and therefore not followed throughout the study), the non-target lesion response at each assessment will be considered ‘not applicable (NA)’.

14.1.37 Study/project specific programming

The standard analysis programs need to be adapted for each study/project.

14.1.38 Censoring reason

In order to summarize the various reasons for censoring, the following categories will be calculated for each time to event variable based on the treatment completion page, the study evaluation completion page and the survival page.

For survival the following censoring reasons are possible:

- Alive
- Lost to follow-up

For PFS and TTP (and therefore duration of responses) the following censoring reasons are possible:

- Ongoing without event
- Lost to follow-up
- Withdrew consent
- Adequate assessment no longer available*
- Event documented after two or more missing tumor assessments (optional, see [Table 14-5](#))
- Death due to reason other than underlying cancer (*only used for TTP and duration of response*)
- Initiation of new anti-cancer therapy

*Adequate assessment is defined in [Section 14.1.24](#). This reason is applicable when adequate evaluations are missing for a specified period prior to data cut-off (or prior to any other censoring reason) corresponding to the unavailability of two or more planned tumor assessments prior to the cut-off date. The following clarifications concerning this reason should also be noted:

- This may be when there has been a definite decision to stop evaluation (e.g. reason=“Sponsor decision” on study evaluation completion page), when patients are not followed for progression after treatment completion or when only UNK assessments are available just prior to data cut-off).

- The reason "Adequate assessment no longer available" also prevails in situations when another censoring reason (e.g. withdrawal of consent, loss to follow-up or alternative anticancer therapy) has occurred more than the specified period following the last adequate assessment.
- This reason will also be used to censor in case of no baseline assessment.

1.1 Reporting Conventions

The following reporting conventions will be adopted for the SAP. These conventions will enhance the review process and help to standardize presentation with common notations. Details regarding the specific TFL numbers, title and body content of the TFL, and any footnote(s) are provided in the section that follows.

- All data listings will be presented in Landscape Orientation.
- Figures will be in black and white, unless otherwise requested. Symbols on figures will not be filled. Lines will be wide enough to see the line after being copied.
- Completely missing values for both numeric and character variables will be explicitly labeled as missing in tables and data listings.
- All analysis programs developed for a table, figure, or data listing will have the name of the program and a date/time stamp on the bottom of each output.
- All analysis programs developed for a table, figure, or data listing display will be self-contained to facilitate transfer of programs. It is recommended that a 1:1 relationship between table and analysis program is used to facilitate this convention.

1.2 TLF Shells

Each table/figure/listing (TFL) produced for the EVEREXES study will have the following general layout. **Bolded text** will appear on each page of the TFL. Details regarding the specific TFL numbers, title and body content of the TFL, and any footnote(s) are provided in the pages that follow.

Novartis
 EVEREXES Study

Page x of y

Category/Variable	Column Header 1 N=XXX	Additional Column Headers (If Applicable) N=XXX
Category ^{a,b} , unit		
Observed, n (%)	xx (xx.x)	xx (xx.x)
Sub-category 1	xx (xx.x)	xx (xx.x)
Sub category 2	xx (xx.x)	xx (xx.x)
Sub category 3	xx (xx.x)	xx (xx.x)
Sub category 4	xx (xx.x)	xx (xx.x)
Variable ^c		
Observed, n (%)	xxx (xx.x)	xxx (xx.x)
Mean (SD)	xx.x (xx.xx)	xx.x (xx.xx)
Median	xx.x	xx.x
Min, Max	xx, xx	xx, xx

a Footnote.

b Another footnote.

c Yet another footnote.

Source Data:xxxx

Program path: x:\xxx\xxx\xxx.sas (9.2) (ddmmmyyyy hh:mm)

Table 1.1 Population Sets and Screening Failures Overall and in Asian subgroup – All Patients

	Statistic	Asian (N=xxx)		Non-Asian (N=xxx)		Total (N=xxx)	
		Overall	Enrolled on or after 01 July 2014	Overall	Enrolled on or after 01 July 2014	Overall	Enrolled on or after 01 July 2014
Number of Screened Patients	n	xxx	xxx	xxx	xxx	xxx	xxx
Number of Screened Failures	n	xxx	xxx	xxx	xxx	xxx	xxx
Unacceptable past medical history/concomitant diagnosis	n (%)	xx (xx.x)	xx (xx.x)	xx (xx.x)	xx (xx.x)	xx (xx.x)	xx (xx.x)
Intercurrent medical event	n (%)	xx (xx.x)	xx (xx.x)	xx (xx.x)	xx (xx.x)	xx (xx.x)	xx (xx.x)
Unacceptable laboratory value	n (%)	xx (xx.x)	xx (xx.x)	xx (xx.x)	xx (xx.x)	xx (xx.x)	xx (xx.x)
Unacceptable test procedure result(s)	n (%)	xx (xx.x)	xx (xx.x)	xx (xx.x)	xx (xx.x)	xx (xx.x)	xx (xx.x)
Did not meet diagnostic/severity criteria	n (%)	xx (xx.x)	xx (xx.x)	xx (xx.x)	xx (xx.x)	xx (xx.x)	xx (xx.x)
Unacceptable use of excluded medication/therapies	n (%)	xx (xx.x)	xx (xx.x)	xx (xx.x)	xx (xx.x)	xx (xx.x)	xx (xx.x)
Patient withdrew consent	n (%)	xx (xx.x)	xx (xx.x)	xx (xx.x)	xx (xx.x)	xx (xx.x)	xx (xx.x)
Unknown	n (%)	xx (xx.x)	xx (xx.x)	xx (xx.x)	xx (xx.x)	xx (xx.x)	xx (xx.x)
Others	n (%)	xx (xx.x)	xx (xx.x)	xx (xx.x)	xx (xx.x)	xx (xx.x)	xx (xx.x)
Number of Enrolled Patients	n	xxx	xxx	xxx	xxx	xxx	xxx
Number of Patients in Full Analysis Set	n (%)	xx (xx.x)	xx (xx.x)	xx (xx.x)	xx (xx.x)	xx (xx.x)	xx (xx.x)
Number of Patients in Per Protocol Set	n (%)	xx (xx.x)	xx (xx.x)	xx (xx.x)	xx (xx.x)	xx (xx.x)	xx (xx.x)
Number of Patients in Safety Set	n (%)	xx (xx.x)	xx (xx.x)	xx (xx.x)	xx (xx.x)	xx (xx.x)	xx (xx.x)

Asian: Indonesia, India, Vietnam, Turkey, South Korea, Thailand, Malaysia, Taiwan or Jordan.

Non-Asian: Australia, Morocco, South Africa or Tunisia.

Table 1.2 Population Sets by Country - All Patients

Country	Enrolled n (%)	Full Analysis Set n (%)	Per Protocol Set n (%)	Safety Set n (%)
TOTAL	XXX	XXX	XXX	XXX
Australia, n (%)	xx (xx.x)	xx (xx.x)	xx (xx.x)	xx (xx.x)
:	:	:	:	:
Vietnam, n (%)	xx (xx.x)	xx (xx.x)	xx (xx.x)	xx (xx.x)

Note to programmer: This table will include the following countries in alphabetical order: Indonesia, India, Vietnam, Turkey, South Korea, Thailand, Malaysia, Taiwan, Jordan, Australia, Morocco, South Africa or Tunisia.

Table 1.3 Patients Disposition Overall and in Asian Subgroup – All patients

Disposition Reason	Asian (N=xx)	Non-Asian (N=xx)	Total (N=xx)
Patients enrolled, n (%)	xx (xx.x)	xx (xx.x)	xx (xx.x)
Untreated	xx (xx.x)	xx (xx.x)	xx (xx.x)
Treated	xx (xx.x)	xx (xx.x)	xx (xx.x)
Patients treated, n (%)	xx (xx.x)	xx (xx.x)	xx (xx.x)
Treatment ongoing	xx (xx.x)	xx (xx.x)	xx (xx.x)
End of treatment	xx (xx.x)	xx (xx.x)	xx (xx.x)
Primary reason for end of treatment	xx (xx.x)	xx (xx.x)	xx (xx.x)
Unacceptable adverse events	xx (xx.x)	xx (xx.x)	xx (xx.x)
Abnormal laboratory value(s)	xx (xx.x)	xx (xx.x)	xx (xx.x)
Abnormal test procedure result(s)	xx (xx.x)	xx (xx.x)	xx (xx.x)
Intercurrent illness that prevent further administration of everolimus treatment	xx (xx.x)	xx (xx.x)	xx (xx.x)
Consent withdrawal	xx (xx.x)	xx (xx.x)	xx (xx.x)
Lost to follow-up	xx (xx.x)	xx (xx.x)	xx (xx.x)
Administrative problems	xx (xx.x)	xx (xx.x)	xx (xx.x)
Death	xx (xx.x)	xx (xx.x)	xx (xx.x)
Disease progression	xx (xx.x)	xx (xx.x)	xx (xx.x)
Treatment duration completed within the scope of Expanded Access. Program (EAP) (till 31 DEC 2014)	xx (xx.x)	xx (xx.x)	xx (xx.x)
Patient is switched to commercial drug	xx (xx.x)	xx (xx.x)	xx (xx.x)
General or specific changes in the patient's condition which render the patient unacceptable for further everolimus treatment at the discretion of the investigator	xx (xx.x)	xx (xx.x)	xx (xx.x)
Need for any other types of anticancer therapy, except for palliative radiotherapy for bone lesions	xx (xx.x)	xx (xx.x)	xx (xx.x)
Everolimus dose interruption of > 4weeks	xx (xx.x)	xx (xx.x)	xx (xx.x)
Length of follow-up from screening to end of study (weeks) ^a			
n	xx	xx	xx
Mean (SD)	xx.x (xx.x)	xx.x (xx.x)	xx.x (xx.x)
Median	xx.x	xx.x	xx.x
Min, Max	xx.x, xx.x	xx.x, xx.x	xx.x, xx.x

Asian: Indonesia, India, Vietnam, Turkey, South Korea, Thailand, Malaysia, Taiwan or Jordan.

Non-Asian: Australia, Morocco, South Africa or Tunisia.

^a Follow-up time: Time from screening visit date to end of study date.

Table 1.4.1 Patients Discontinuing Study Treatment by Visit – Full Analysis Set

STATUS Reason, n (%)	VISIT							
	Baseline	WK 4	WK 10	WK 20	WK 30	WK 40	WK 50	EOT
Total (N=xxx)	xxx	xxx	xxx	xxx	xxx	xxx	xxx	xxx
End of Study Treatment								
Unacceptable adverse events	xx (xx.x)	xx (xx.x)	xx (xx.x)	xx (xx.x)	xx (xx.x)	xx (xx.x)	xx (xx.x)	xx (xx.x)
Abnormal laboratory value(s)	xx (xx.x)	xx (xx.x)	xx (xx.x)	xx (xx.x)	xx (xx.x)	xx (xx.x)	xx (xx.x)	xx (xx.x)
Abnormal test procedure result(s)	xx (xx.x)	xx (xx.x)	xx (xx.x)	xx (xx.x)	xx (xx.x)	xx (xx.x)	xx (xx.x)	xx (xx.x)
Intercurrent illness that prevent further administration of everolimus treatment	xx (xx.x)	xx (xx.x)	xx (xx.x)	xx (xx.x)	xx (xx.x)	xx (xx.x)	xx (xx.x)	xx (xx.x)
Consent withdrawal	xx (xx.x)	xx (xx.x)	xx (xx.x)	xx (xx.x)	xx (xx.x)	xx (xx.x)	xx (xx.x)	xx (xx.x)
Lost to follow-up	xx (xx.x)	xx (xx.x)	xx (xx.x)	xx (xx.x)	xx (xx.x)	xx (xx.x)	xx (xx.x)	xx (xx.x)
Administrative problems	xx (xx.x)	xx (xx.x)	xx (xx.x)	xx (xx.x)	xx (xx.x)	xx (xx.x)	xx (xx.x)	xx (xx.x)
Death	xx (xx.x)	xx (xx.x)	xx (xx.x)	xx (xx.x)	xx (xx.x)	xx (xx.x)	xx (xx.x)	xx (xx.x)
Disease progression	xx (xx.x)	xx (xx.x)	xx (xx.x)	xx (xx.x)	xx (xx.x)	xx (xx.x)	xx (xx.x)	xx (xx.x)
Treatment duration completed within the scope of Expanded Access Program (EAP) (till 31 DEC 2014)	xx (xx.x)	xx (xx.x)	xx (xx.x)	xx (xx.x)	xx (xx.x)	xx (xx.x)	xx (xx.x)	xx (xx.x)
Patient is switched to commercial drug	xx (xx.x)	xx (xx.x)	xx (xx.x)	xx (xx.x)	xx (xx.x)	xx (xx.x)	xx (xx.x)	xx (xx.x)
General or specific changes in the patient's condition which render the patient unacceptable for further everolimus treatment at the discretion of the investigator	xx (xx.x)	xx (xx.x)	xx (xx.x)	xx (xx.x)	xx (xx.x)	xx (xx.x)	xx (xx.x)	xx (xx.x)
Need for any other types of anticancer therapy, except for palliative radiotherapy for bone lesions	xx (xx.x)	xx (xx.x)	xx (xx.x)	xx (xx.x)	xx (xx.x)	xx (xx.x)	xx (xx.x)	xx (xx.x)
Everolimus dose interruption of > 4weeks	xx (xx.x)	xx (xx.x)	xx (xx.x)	xx (xx.x)	xx (xx.x)	xx (xx.x)	xx (xx.x)	xx (xx.x)

EOT: End of Treatment.

Table 1.4.2 Patients Discontinuing Study Treatment by Visit for Asian Patients – Full Analysis Set

Asian: Indonesia, India, Vietnam, Turkey, South Korea, Thailand, Malaysia, Taiwan or Jordan.

EOT: End of Treatment.

Table 1.4.3 Patients Discontinuing Study Treatment by Visit for Non-Asian Patients – Full Analysis Set

Non-Asian: Australia, Morocco, South Africa or Tunisia.

EOT: End of Treatment.

These tables will be created using the same layout as Table 1.4.1.

Table 1.5.1 Study Evaluation Completion Status by Visit – Full Analysis Set

STATUS Reason, n (%)	VISIT								
	Baseline	WK 4	WK 10	WK 20	WK 30	WK 40	WK 50	EOT	Overall
Total (N=xxx)	xxx	xxx	xxx	xxx	xxx	xxx	xxx	xxx	xxx
Study Evaluation Completion	xxx	xxx	xxx	xxx	xxx	xxx	xxx	xxx	xxx
Patient withdrew consent	xx (xx.x)	xx (xx.x)	xx (xx.x)	xx (xx.x)	xx (xx.x)	xx (xx.x)	xx (xx.x)	xx (xx.x)	xx (xx.x)
Lost to follow-up	xx (xx.x)	xx (xx.x)	xx (xx.x)	xx (xx.x)	xx (xx.x)	xx (xx.x)	xx (xx.x)	xx (xx.x)	xx (xx.x)
Administrative problems	xx (xx.x)	xx (xx.x)	xx (xx.x)	xx (xx.x)	xx (xx.x)	xx (xx.x)	xx (xx.x)	xx (xx.x)	xx (xx.x)
Death	xx (xx.x)	xx (xx.x)	xx (xx.x)	xx (xx.x)	xx (xx.x)	xx (xx.x)	xx (xx.x)	xx (xx.x)	xx (xx.x)
New cancer therapy	xx (xx.x)	xx (xx.x)	xx (xx.x)	xx (xx.x)	xx (xx.x)	xx (xx.x)	xx (xx.x)	xx (xx.x)	xx (xx.x)
Disease progression	xx (xx.x)	xx (xx.x)	xx (xx.x)	xx (xx.x)	xx (xx.x)	xx (xx.x)	xx (xx.x)	xx (xx.x)	xx (xx.x)
Patient is switched to commercial drug	xx (xx.x)	xx (xx.x)	xx (xx.x)	xx (xx.x)	xx (xx.x)	xx (xx.x)	xx (xx.x)	xx (xx.x)	xx (xx.x)
Other	xx (xx.x)	xx (xx.x)	xx (xx.x)	xx (xx.x)	xx (xx.x)	xx (xx.x)	xx (xx.x)	xx (xx.x)	xx (xx.x)

EOT: End Of Treatment.

Table 1.5.2 Study Evaluation Completion Status by Visit for Asian Patients – Full Analysis Set

Asian: Indonesia, India, Vietnam, Turkey, South Korea, Thailand, Malaysia, Taiwan or Jordan.

EOT: End of Treatment.

Table 1.5.3 Study Evaluation Completion Status by Visit for Non-Asian Patients – Full Analysis Set

Non-Asian: Australia, Morocco, South Africa or Tunisia.

EOT: End of Treatment.

These tables will be created using the same layout as Table 1.5.1.

Table 1.6 Major Protocol Deviations Overall and in Asian subgroup – Full Analysis Set

Major Protocol Deviations	Asian (N=xx)	Non-Asian (N=xx)	Total (N=xx)
Major Protocol Violations, n (%)	xx (xx.x)	xx (xx.x)	xx (xx.x)
Violation of eligibility criteria	xx (xx.x)	xx (xx.x)	xx (xx.x)
Violation of any inclusion criteria	xx (xx.x)	xx (xx.x)	xx (xx.x)
Violation of any exclusion criteria	xx (xx.x)	xx (xx.x)	xx (xx.x)
Informed consent from (ICF) not signed	xx (xx.x)	xx (xx.x)	xx (xx.x)
Date of ICF prior to date of first visit/procedure	xx (xx.x)	xx (xx.x)	xx (xx.x)
Patients without metastatic or locally advanced breast cancer	xx (xx.x)	xx (xx.x)	xx (xx.x)
Hormone Receptor non-positive at screening	xx (xx.x)	xx (xx.x)	xx (xx.x)
ECOG performance at baseline status higher than 2	xx (xx.x)	xx (xx.x)	xx (xx.x)
Patient receive a prohibited medication	xx (xx.x)	xx (xx.x)	xx (xx.x)

Asian: Indonesia, India, Vietnam, Turkey, South Korea, Thailand, Malaysia, Taiwan or Jordan.

Non-Asian: Australia, Morocco, South Africa or Tunisia.

Table 2.1.1 Patient Demographics Overall and in Asian Subgroup – Full Analysis Set

	Asian (N=xx)	Non-Asian (N=xx)	Total (N=xx)
Age at informed consent (years)			
n	xx	xx	xx
Mean (SD)	xx.x (xx.x)	xx.x (xx.x)	xx.x (xx.x)
95% CI	xx.x, xx.x	xx.x, xx.x	xx.x, xx.x
Median	xx.x	xx.x	xx.x
Min, Max	xx.x, xx.x	xx.x, xx.x	xx.x, xx.x
Gender, n (%)			
n	xx	xx	xx
Men	xx (xx.x)	xx (xx.x)	xx (xx.x)
Women	xx (xx.x)	xx (xx.x)	xx (xx.x)
Race, n (%)			
n	---	---	xx
Caucasian	---	---	xx (xx.x)
Asian	---	---	xx (xx.x)
Other ¹	---	---	xx (xx.x)
Ethnicity, n (%)			
n	xx	xx	xx
Hispanic/Latino	xx (xx.x)	xx (xx.x)	xx (xx.x)
Chinese	xx (xx.x)	xx (xx.x)	xx (xx.x)
Indian (Indian subcontinent)	xx (xx.x)	xx (xx.x)	xx (xx.x)
Japanese	xx (xx.x)	xx (xx.x)	xx (xx.x)
Mixed ethnicity	xx (xx.x)	xx (xx.x)	xx (xx.x)
Other	xx (xx.x)	xx (xx.x)	xx (xx.x)

CI: Confidence Interval, SD: Standard Deviation.

Asian: Indonesia, India, Vietnam, Turkey, South Korea, Thailand, Malaysia, Taiwan or Jordan.

Non-Asian: Australia, Morocco, South Africa or Tunisia.

1. Other includes the sub-categories of Black, Native American, Pacific Islander and Other.

Table 2.1.2 Baseline Clinical Characteristics Overall and in Asian Subgroup – Full Analysis Set

	Asian (N=xxx)	Non-Asian (N=xxx)	Total (N=xxx)
Height, cm			
n	xx	xx	xx
Mean (SD)	xx.x (xx.x)	xx.x (xx.x)	xx.x (xx.x)
Median	xx.x	xx.x	xx.x
Min, Max	xx.x, xx.x	xx.x, xx.x	xx.x, xx.x
Weight, kg			
n	xx	xx	xx
Mean (SD)	xx.x (xx.x)	xx.x (xx.x)	xx.x (xx.x)
Median	xx.x	xx.x	xx.x
Min, Max	xx.x, xx.x	xx.x, xx.x	xx.x, xx.x
Body Mass Index (BMI), kg/m ²			
n	xx	xx	xx
Mean (SD)	xx.x (xx.x)	xx.x (xx.x)	xx.x (xx.x)
Median	xx.x	xx.x	xx.x
Min, Max	xx.x, xx.x	xx.x, xx.x	xx.x, xx.x
Body temperature, °C			
n	xx	xx	xx
Mean (SD)	xx.x (xx.x)	xx.x (xx.x)	xx.x (xx.x)
Median	xx.x	xx.x	xx.x
Min, Max	xx.x, xx.x	xx.x, xx.x	xx.x, xx.x
Heart rate, bpm			
n	xx	xx	xx
Mean (SD)	xx.x (xx.x)	xx.x (xx.x)	xx.x (xx.x)
Median	xx.x	xx.x	xx.x
Min, Max	xx.x, xx.x	xx.x, xx.x	xx.x, xx.x
Systolic blood pressure (SBP), mmHg			
n	xx	xx	xx
Mean (SD)	xx.x (xx.x)	xx.x (xx.x)	xx.x (xx.x)
Median	xx.x	xx.x	xx.x
Min, Max	xx.x, xx.x	xx.x, xx.x	xx.x, xx.x
Diastolic blood pressure (DBP), mmHg			
n	xx	xx	xx
Mean (SD)	xx.x (xx.x)	xx.x (xx.x)	xx.x (xx.x)
Median	xx.x	xx.x	xx.x

	Asian (N=xxx)	Non-Asian (N=xxx)	Total (N=xxx)
Min, Max	xx.x, xx.x	xx.x, xx.x	xx.x, xx.x
ECOG performance status, n (%)			
n	xx	xx	xx
0	xx (xx.x)	xx (xx.x)	xx (xx.x)
1	xx (xx.x)	xx (xx.x)	xx (xx.x)
>= 2	xx (xx.x)	xx (xx.x)	xx (xx.x)
Estrogen receptor, n (%)			
n	xx	xx	xx
Positive	xx (xx.x)	xx (xx.x)	xx (xx.x)
Negative	xx (xx.x)	xx (xx.x)	xx (xx.x)
Not assessable	xx (xx.x)	xx (xx.x)	xx (xx.x)
Progesterone receptor, n (%)			
n	xx	xx	xx
Positive	xx (xx.x)	xx (xx.x)	xx (xx.x)
Negative	xx (xx.x)	xx (xx.x)	xx (xx.x)
Not assessable	xx (xx.x)	xx (xx.x)	xx (xx.x)
Measurable disease ¹ or bone lesions, n (%)			
n	xx	xx	xx
No	xx (xx.x)	xx (xx.x)	xx (xx.x)
Yes	xx (xx.x)	xx (xx.x)	xx (xx.x)
Metastatic sites, n (%)			
n	xx	xx	xx
Lung and/or liver	xx (xx.x)	xx (xx.x)	xx (xx.x)
Bone	xx (xx.x)	xx (xx.x)	xx (xx.x)
Bone only	xx (xx.x)	xx (xx.x)	xx (xx.x)

CI: Confidence Interval, SD: Standard Deviation, ECOG: Eastern Cooperative Oncology Group, BMI=Weight(kg)/[Height(m)]². bpm: beats per minute. CT: Computed Tomography. MRI: Magnetic Resonance Imaging.

Asian: Indonesia, India, Vietnam, Turkey, South Korea, Thailand, Malaysia, Taiwan or Jordan.

Non-Asian: Australia, Morocco, South Africa or Tunisia.

1. Measurable disease defined as at least one lesion that can be accurately measured in at least one dimension = 20 mm with conventional imaging techniques or = 10 mm with spiral CT or MRI.

Table 2.1.3 Baseline Prior Treatment Overall and in Asian Subgroup – Full Analysis Set

	Asian (N=xx)	Non-Asian (N=xx)	Total (N=xx)
Sensitivity to previous endocrine therapy ¹ , n (%)			
n	xx	xx	xx
No	xx (xx.x)	xx (xx.x)	xx (xx.x)
Yes	xx (xx.x)	xx (xx.x)	xx (xx.x)
Purpose of most recent treatment, n (%)			
n	xx	xx	xx
Adjuvant therapy	xx (xx.x)	xx (xx.x)	xx (xx.x)
Therapy for advanced/metastatic disease	xx (xx.x)	xx (xx.x)	xx (xx.x)
ANA or LET as most recent treatment, n (%)			
n	xx	xx	xx
No	xx (xx.x)	xx (xx.x)	xx (xx.x)
Yes	xx (xx.x)	xx (xx.x)	xx (xx.x)
Previous tamoxifen treatment, n (%)			
n	xx	xx	xx
No	xx (xx.x)	xx (xx.x)	xx (xx.x)
Yes	xx (xx.x)	xx (xx.x)	xx (xx.x)
Previous fulvestrant treatment, n (%)			
n	xx	xx	xx
No	xx (xx.x)	xx (xx.x)	xx (xx.x)
Yes	xx (xx.x)	xx (xx.x)	xx (xx.x)
Any previous use of chemotherapy, n (%)			
n	xx	xx	xx
No	xx (xx.x)	xx (xx.x)	xx (xx.x)
Yes	xx (xx.x)	xx (xx.x)	xx (xx.x)
Number of prior systemic therapies (in adjuvant or metastatic setting), n (%)			
n	xx	xx	xx
0	xx (xx.x)	xx (xx.x)	xx (xx.x)
1	xx (xx.x)	xx (xx.x)	xx (xx.x)
>=2	xx (xx.x)	xx (xx.x)	xx (xx.x)
Number of prior systemic treatment (chemotherapies or hormonal therapies) in metastatic setting (excluding adjuvant and neoadjuvant setting), n (%)			
n	xx	xx	xx
0	xx (xx.x)	xx (xx.x)	xx (xx.x)

	Asian (N=xx)	Non-Asian (N=xx)	Total (N=xx)
1	xx (xx.x)	xx (xx.x)	xx (xx.x)
>=2	xx (xx.x)	xx (xx.x)	xx (xx.x)
Prior chemotherapies in metastatic setting (excluding adjuvant and neoadjuvant setting), n (%)			
n	xx	xx	xx
Yes	xx (xx.x)	xx (xx.x)	xx (xx.x)
No	xx (xx.x)	xx (xx.x)	xx (xx.x)

ANA: Anastrozole. LET: Letrozole. BC: Breast Cancer.

Asian: Indonesia, India, Vietnam, Turkey, South Korea, Thailand, Malaysia, Taiwan or Jordan.

Non-Asian: Australia, Morocco, South Africa or Tunisia.

1. Defined as at least 24 months of endocrine therapy before recurrence in the adjuvant setting or a response or stabilization for at least 24 weeks of endocrine therapy for advanced disease

2. Prior therapies include those used in the adjuvant setting or to treat advanced disease.

Table 2.2 Prior Antineoplastic Therapy Overall and in Asian Subgroup - Full Analysis Set

Antineoplastic therapy	Asian (N=xx)	Non-Asian (N=xx)	Total (N=xxx)
Patients with no prior procedures, n (%)	xx (xx.x)	xx (xx.x)	xx (xx.x)
Patients with at least one prior procedure, n (%)	xx (xx.x)	xx (xx.x)	xx (xx.x)
Surgery, n (%)	xx (xx.x)	xx (xx.x)	xx (xx.x)
Lumpectomy	xx (xx.x)	xx (xx.x)	xx (xx.x)
Segmentectomy	xx (xx.x)	xx (xx.x)	xx (xx.x)
Mastectomy	xx (xx.x)	xx (xx.x)	xx (xx.x)
Other	xx (xx.x)	xx (xx.x)	xx (xx.x)
Radiotherapy, n (%) ¹	xx (xx.x)	xx (xx.x)	xx (xx.x)
Medications (solid tumors), n (%) ²	xx (xx.x)	xx (xx.x)	xx (xx.x)
Chemotherapy	xx (xx.x)	xx (xx.x)	xx (xx.x)
Hormonal therapy	xx (xx.x)	xx (xx.x)	xx (xx.x)
Immunotherapy	xx (xx.x)	xx (xx.x)	xx (xx.x)
Targeted therapy	xx (xx.x)	xx (xx.x)	xx (xx.x)
Other	xx (xx.x)	xx (xx.x)	xx (xx.x)

Asian: Indonesia, India, Vietnam, Turkey, South Korea, Thailand, Malaysia, Taiwan or Jordan.

Non-Asian: Australia, Morocco, South Africa or Tunisia.

1. Including all settings: adjuvant, neoadjuvant, therapeutic, prevention and symptom control.

2. Including all settings: adjuvant, neoadjuvant, therapeutic and prevention.

Table 2.3 Prior Medications Overall and in Asian Subgroup - Full Analysis Set

Anatomic Therapeutic Category (ATC)*/ Preferred Term	Asian (N=xx)	Non-Asian (N=xx)	Total (N=xxx)
Patients with no prior medications, n (%)	xx (xx.x)	xx (xx.x)	xx (xx.x)
Patients with at least one prior medication, n (%)	xx (xx.x)	xx (xx.x)	xx (xx.x)
ATC CLASSIFICATION, n (%) ¹	xx (xx.x)	xx (xx.x)	xx (xx.x)
Preferred Term 1	xx (xx.x)	xx (xx.x)	xx (xx.x)
Preferred Term N	xx (xx.x)	xx (xx.x)	xx (xx.x)
ATC CLASSIFICATION, n (%) ¹	xx (xx.x)	xx (xx.x)	xx (xx.x)
Preferred Term 1	xx (xx.x)	xx (xx.x)	xx (xx.x)
Preferred Term N	xx (xx.x)	xx (xx.x)	xx (xx.x)
Etc.			

Asian: Indonesia, India, Vietnam, Turkey, South Korea, Thailand, Malaysia, Taiwan or Jordan.

Non-Asian: Australia, Morocco, South Africa or Tunisia.

* Prior medications taken within the last 4 weeks prior to day 1 are coded to preferred terms and classifications using the WHO-Drug Dictionary. A patient with more than one medication for a preferred term (PT) or ATC classification is counted only once for that PT or ATC classification.

1. Percentages calculated from patients with at least one prior medication. A patient could show more than one PT within the same ATC classification. These are not exclusive. Consequently, the sum of percentages within an ATC classification could be higher than 100%.

Table 2.4 Concomitant Medications Overall and in Asian Subgroup - Full Analysis Set

Anatomic Therapeutic Category (ATC)*/ Preferred Term	Asian (N=xx)	Non-Asian (N=xx)	Total (N=xxx)
Patients with no concomitant medications, n (%)	xx (xx.x)	xx (xx.x)	xx (xx.x)
Patients with at least one concomitant medication, n (%)	xx (xx.x)	xx (xx.x)	xx (xx.x)
ATC CLASSIFICATION, n (%) ¹	xx (xx.x)	xx (xx.x)	xx (xx.x)
Preferred Term 1	xx (xx.x)	xx (xx.x)	xx (xx.x)
Preferred Term N	xx (xx.x)	xx (xx.x)	xx (xx.x)
ATC CLASSIFICATION, n (%) ¹	xx (xx.x)	xx (xx.x)	xx (xx.x)
Preferred Term 1	xx (xx.x)	xx (xx.x)	xx (xx.x)
Preferred Term N	xx (xx.x)	xx (xx.x)	xx (xx.x)
Etc.			

Asian: Indonesia, India, Vietnam, Turkey, South Korea, Thailand, Malaysia, Taiwan or Jordan.

Non-Asian: Australia, Morocco, South Africa or Tunisia.

* Concomitant medications taken from day 1 are coded to preferred terms and classifications using the WHO-Drug Dictionary. A patient with more than one medication for a preferred term (PT) or ATC classification is counted only once for that PT or ATC classification.

1. Percentages calculated from patients with at least one concomitant medication. A patient could show more than one PT within the same ATC classification. These are not exclusive. Consequently, the sum of percentages within an ATC classification could be higher than 100%.

Table 2.5 Medical History Overall and in Asian Subgroup - Full Analysis Set

System Organ Class*/ Preferred Term	Asian (N=xx)	Non-Asian (N=xx)	Total (N=xxx)
Patients with no medical history abnormalities, n (%)	xx (xx.x)	xx (xx.x)	xx (xx.x)
Patients with at least one medical history abnormality, n (%)	xx (xx.x)	xx (xx.x)	xx (xx.x)
SYSTEM ORGAN CLASS 1, n (%) ¹	xx (xx.x)	xx (xx.x)	xx (xx.x)
Preferred Term 1	xx (xx.x)	xx (xx.x)	xx (xx.x)
Preferred Term N	xx (xx.x)	xx (xx.x)	xx (xx.x)
SYSTEM ORGAN CLASS 2, n (%) ¹	xx (xx.x)	xx (xx.x)	xx (xx.x)
Preferred Term 1	xx (xx.x)	xx (xx.x)	xx (xx.x)
Preferred Term N	xx (xx.x)	xx (xx.x)	xx (xx.x)

Etc.

Asian: Indonesia, India, Vietnam, Turkey, South Korea, Thailand, Malaysia, Taiwan or Jordan.

Non-Asian: Australia, Morocco, South Africa or Tunisia.

*Medical abnormalities are coded using MedDRA version 19.1. A patient with more than one medical condition for a preferred term (PT) or system organ class (SOC) is counted only once for that PT or SOC.

1. Percentages calculated from patients with at least one medical history abnormality. A patient could show more than one PT within the same SOC. These are not exclusive. Consequently, the sum of percentages within a SOC could be higher than 100%.

Table 3.1 Patient Disease History Overall and in Asian Subgroup - Full Analysis Set

	Asian (N=xx)	Non-Asian (N=xx)	Total (N=xxx)
Primary site of cancer, n (%)			
Breast	xx (xx.x)	xx (xx.x)	xx (xx.x)
Details of tumor histology / cytology, n (%)			
n	xxxx	xxxx	xxxx
Invasive ductal carcinoma	xx (xx.x)	xx (xx.x)	xx (xx.x)
Invasive lobular carcinoma	xx (xx.x)	xx (xx.x)	xx (xx.x)
Other	xx (xx.x)	xx (xx.x)	xx (xx.x)
NA	xx (xx.x)	xx (xx.x)	xx (xx.x)
Time since initial diagnosis of cancer (years) ¹			
n	xxxx	xxxx	xxxx
Mean (SD)	xx.x (xx.x)	xx.x (xx.x)	xx.x (xx.x)
Median	xx.x	xx.x	xx.x
Min, Max	xx.x, xx.x	xx.x, xx.x	xx.x, xx.x
Time to first recurrence/metastasis (days) ¹			
n	xxxx	xxxx	xxxx
